2.1.1.4 Unscheduled visits

For tabulation and analyses by visit, all data collected at the unscheduled visits will first be allocated to a nearest planned main visit, then taken into account as the data (or part of the data) for that visit ([Section 2.1.1.3](#)). For analyses showing abnormalities, data from unscheduled visits will be considered individually, without mapping to a main visit.

All data collected at unscheduled visits will be listed.

2.1.1.5 On-treatment period

The on-treatment period lasts from the date of first administration of study treatment to 30 days after the date of the last actual administration of any study treatment, i.e., date of the last actual administration of any study treatment (from 'Study treatment' CRF) – date of first administration of study treatment (from 'Study treatment' CRF) +1 + 30.

2.1.1.6 Missing baseline data

Missing baseline data will not be imputed.

2.1.1.7 Missing post-baseline data

Observations with values 'not done', 'not evaluable', 'not applicable' will be treated as missing values.

2.1.1.8 Better-seeing and worse-seeing eyes

The worse-seeing eye is defined as the eye that has the lower monocular DCNVA ETDRS letter score at baseline and the better-seeing eye is defined as the eye that has the higher ETDRS letter score. For subjects with identical monocular DCNVA ETDRS letter scores for both eyes at baseline, the right eye is defined as the worse-seeing eye.

2.2 Analysis sets

The **Full Analysis Set** (FAS) comprises all subjects to whom study treatment has been assigned by randomization. According to the intent to treat principle, subjects will be analyzed according to the treatment and strata they have been assigned to during the randomization procedure. FAS will be used for all efficacy variables, unless otherwise stated.

The **Safety Set** (SAF) includes all subjects who received at least one dose of study treatment. Subjects will be analyzed according to the study treatment received, where treatment received is defined as the randomized/assigned treatment if the subject took at least one dose of that treatment or the first treatment received if the randomized/assigned treatment was never administered.

Rules of exclusion criteria of analysis sets with protocol deviations and subject classification are specified in [Appendix 5.3](#).

The number and percentage of subjects within each of the above analysis sets will be summarized.

[REDACTED]

2.3 Subject disposition, demographics and other baseline characteristics

2.3.1 Subject disposition

Subject disposition will be summarized separately by treatment group and total for the FAS. Specifically, the number and proportion of subjects who discontinued the study will be summarized by treatment and total. The primary reason for premature study discontinuation will be summarized in the table.

In addition, protocol deviations (PDs) will be summarized through presenting the number and percentage of subjects with each deviation.

2.3.2 Subject demographics and other baseline characteristics

Demographic (including age, sex, race, ethnicity) and other baseline data including disease characteristics (including DCNVA, best-corrected distance visual acuity [BCDVA], [REDACTED]) will be listed and summarized descriptively by treatment group for the FAS.

Categorical data will be presented as frequencies and percentages. For continuous data, mean, standard deviation, median, minimum, and maximum will be presented.

Relevant medical histories and current medical conditions at baseline will be summarized by system organ class, preferred term and treatment group separately for ocular and non-ocular histories/conditions. This includes any abnormalities noted during baseline evaluation of anterior and posterior eye segment health.

2.4 Treatments (study treatment, rescue medication, concomitant therapies, compliance)

The SAF will be used for the analyses below. Categorical data will be summarized as frequencies and percentages. For continuous data, mean, standard deviation, median, minimum, and maximum will be presented.

2.4.1 Study treatment / compliance

The duration of exposure in days to UNR844-CI or placebo will be summarized by means of descriptive statistics. The duration of exposure in days to UNR844-CI or placebo is defined as: date of the last actual administration of UNR844-CI or placebo (from 'Study treatment' CRF) – date of first administration of UNR844-CI or placebo (from 'Study treatment' CRF) +1.

Moreover, the on-treatment period (corresponding to the safety observation period) will also be summarized descriptively. The definition of the on-treatment period can be found from [Section 2.1.1.5](#).

Compliance will be presented by summarizing the total number of days with any treatment by treatment group. Reason of premature discontinuation from study treatment will also be summarized.

Total number of days with any treatment is calculated from ‘Study treatment’ CRF, by summing number of days ‘Dose interrupted’ and number of days from ‘Dose permanently discontinued’ to study end (the total number of days without treatment), then subtracted by duration of exposure. Suppose a subject has twice with ‘Dose interrupted’ and later ‘Dose permanently discontinued’ as recorded on ‘Study treatment’ CRF, then this subject’s total number of days without treatment is: (Start date of dose after the first dose interruption – stop date of dose before the first dose interruption) + (Start date of dose after the second dose interruption – Stop date of dose before the second dose interruption) + (end of study date – stop date of dose when ‘Dose permanently discontinued’).

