## 8 Visit schedule and assessments

The assessment schedule ([Table 8-1](#)) lists all of the assessments and indicates with an “X” the visits when they are performed. All data obtained from these assessments must be supported in the subject’s source documentation.

[figure not shown]
Subjects should be seen for all visits/assessments as outlined in the assessment schedule ([Table 8-1](#)) or as close to the designated day/time as possible. Screening visit assessments may be split on separate days as close as possible to each other, however all visual acuity and refraction assessments must be performed on the same day. Missed or rescheduled visits should not lead to automatic discontinuation. Subjects who prematurely discontinue the study for any reason should be scheduled for a visit as soon as possible, at which time all of the assessments listed for the final visit will be performed. At this final visit, all dispensed investigational product should be reconciled, and any adverse event and concomitant medications recorded on the eCRF.

All randomized and/or treated subjects should have a safety follow-up call conducted 30 days after last administration of study treatment ([Section 9.2](#)).

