## 9 Study discontinuation and completion

### 9.1 Discontinuation

#### 9.1.1 Discontinuation of study treatment

Discontinuation of study treatment for a subject occurs when study treatment is stopped earlier than the protocol planned duration, and can be initiated by either the subject or the investigator.

The investigator must discontinue study treatment for a given subject if, he/she believes that continuation would negatively impact the subject's well-being.

Study treatment must be discontinued under the following circumstances:

- Subject decision
- Pregnancy
- Use of prohibited medications or therapies as described in [Table 6-2](#)
- Unsatisfactory therapeutic effect
- Any situation in which study participation might result in a safety risk to the subject
- Following emergency unmasking

If discontinuation of study treatment occurs, the investigator should make a reasonable effort to understand the primary reason for the subject's premature discontinuation of study treatment and record this information.

Subjects who discontinue study treatment or who decide they do not wish to participate in the study further should NOT be considered withdrawn from the study UNLESS they withdraw their consent (see [Section 9.1.2](#)). **Where possible, they should return for the assessments indicated in the assessment schedule.** If they fail to return for these assessments for unknown reasons, every effort (e.g., telephone, e-mail, or letter) should be made to contact the subject/pre-designated contact as specified in the lost to follow-up section. This contact should preferably be done according to the study visit schedule.

If the subject cannot or is unwilling to attend any visit(s), the site staff should maintain regular telephone contact with the subject, or with a person pre-designated by the subject. This telephone contact should preferably be done according to the study visit schedule.

After study treatment discontinuation, at a minimum, in abbreviated visits, the following data should be collected at clinic visits or via telephone/email contact:

- New/concomitant treatments
- AEs/SAEs

The investigator must also contact the IRT to register the subject's discontinuation from study treatment.

If discontinuation occurs because treatment code has been broken, please refer to Emergency breaking of treatment code section ([Section 6.6.2](#)).

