2.1.1.3 End of study/end of treatment/unscheduled visit day mapping

The *end of study* date (from ‘Study disposition’ CRF) is the date when a subject completes or discontinues the study. The *end of treatment* date (from ‘Treatment disposition’ CRF) is the date of the last study treatment prior to/on the end of study date. For reporting data by visit in outputs, the end of study with discontinuation (Subject status from ‘Study disposition’ CRF NOT being ‘Completed’)/end of treatment with discontinuation (Subject status from ‘Treatment disposition’ CRF NOT being ‘Completed’)/unscheduled visit date will be allocated to the nearest planned main visit, by a 1/3 – 2/3 rule. To be more specific, suppose such a visit falls in two adjacent scheduled visits (e.g., visits A and B) of an assessment corresponding to visit days of X and Y. If the assessment day of such a visit falls within rounding ($1/3 * (Y - X + 1)$) after Day X, then it will be allocated to visit A, and to visit B otherwise. [Figure 2-1](#) shows a graphical illustration of how this 1/3 – 2/3 rule of visit allocation is done. [Table 2-1](#) shows an example of the allocation of end of study/end of treatment/unscheduled visit to a scheduled main visit, when an assessment is scheduled to be done at every scheduled visit; and [Table 2-2](#) shows another example of visit allocation when an assessment is only done at Baseline, Month 1, 2 and 3.

Figure 2-1 Graphical illustration of visit allocation using the 1/3 – 2/3 rule

[figure not shown]

Table 2-1 Allocation of end of study/end of treatment/unscheduled visit for an assessment to be done at each scheduled visit

Scheduled main visit name/label	Scheduled visit study day	Scheduled visit window in days	Comment
Screening	-7	-7 – -1	Screening
Baseline	1	1	Baseline
W2	14	2 – 19	
M1	30	20 – 35	
M1.5	45	36 – 50	
M2	60	51 – 65	
M2.5	75	66 – 80	
M3	90	>= 81	

Table 2-2 Allocation of end of study/end of treatment/unscheduled visit for an assessment to be done at Baseline, Month 1, 2 and 3

Scheduled main visit name/label	Scheduled visit study day	Scheduled visit window in days	Comment
Baseline	1	1	Baseline
M1	30	2 – 40	
M2	60	41 – 70	
M3	90	>= 71	

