2.5.4 Supportive analyses

There will be two supportive analyses

Supportive analysis #1:

The efficacy endpoint for Supportive analysis #1 is change from baseline in binocular DCNVA at Month 3 regardless of whether or not the intercurrent events occurred. The only difference between this analysis and the primary efficacy analysis is the inclusion of the data points after use of prohibited medications or therapy, prohibited medication changes or treatment discontinuation.

All data collected will be included in this analysis and the same imputation methods as those for the primary efficacy endpoint will be used to impute the time points that the data was truly missing.

Supportive analysis #2:

The efficacy endpoint for Supportive analysis #2 is change from baseline in binocular DCNVA at the end of treatment, i.e., the time when last study treatment is administered, which is always observed. There is no missing data imputation for the efficacy endpoint of this supportive analysis.

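### SAP 2.4.1 subtracts the days after permanent discontinuation from an exposure duration that already ends at the last dose, so days with any treatment come out too low for subjects followed after stopping

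*SAP*

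**What the plan says.** SAP 2.4.1 contains both definitions that matter here.

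- Duration of exposure ends at the "date of the last actual administration of UNR844-CI or placebo". The first-administration date is subtracted and one day is added.
- "Compliance will be presented by summarizing the total number of days with any treatment by treatment group". To derive that total, the SAP sums the interruption days and the days from permanent discontinuation "to study end (the total number of days without treatment), then subtracted by duration of exposure". Its illustration, a subject with two interruptions and then a permanent stop, includes a term equal to the end-of-study date minus the stop date at permanent discontinuation.

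SAP 2.4 sets the statistics to be shown: "For continuous data, mean, standard deviation, median, minimum, and maximum will be presented".

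The documents treat the end of treatment and the end of study as separate events. Under SAP 2.1.1.3 the end-of-treatment date "is the date of the last study treatment prior to/on the end of study date". Protocol 9.1.1 says of subjects who stop study treatment: "Where possible, they should return for the assessments indicated in the assessment schedule". Supportive analysis #1 in SAP 2.5.4 differs from the primary analysis by the "inclusion of the data points after use of prohibited medications or therapy, prohibited medication changes or treatment discontinuation". For subjects who leave the study, Protocol section 8 says: "Subjects who prematurely discontinue the study for any reason should be scheduled for a visit as soon as possible".

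**The concern.** Time off drug can only be deducted from a period that contains it. Interruption days lie between first and last dose, so deducting them from duration of exposure is sound. The days between a permanent stop and the end of study lie after the last dose, outside that duration. Deducting them penalises the subject a second time for stopping early.

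The subjects affected are those who stop drug but stay in the study, as Protocol 9.1.1 asks where possible. A compliance table most needs to describe these subjects correctly. This total is the only quantity the SAP presents as compliance. For such subjects it would disagree with the correctly defined duration of exposure in the same section, and the planned minimum could be a negative number of days.

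**Working it through.** The SAP gives no numerical result for this derivation, so there is no stated figure to reproduce. The check is a day count.

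**Inputs**
- First dose on Day 1 and last dose on Day L, so exposure = L - 1 + 1 = L (SAP 2.4.1).
- End of study on Day E, with E at or after L (SAP 2.1.1.3).
- Post-stop days = E - L (SAP 2.4.1 illustration), assuming the stop date on the permanent-discontinuation record is the last-dose date.
- Day 90 is the scheduled Month 3/end-of-study visit (Protocol Table 8-1). The other days are chosen for illustration.

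**Direction of the subtraction.** Taken literally, the text computes untreated days minus exposure. A Day 90 completer with no untreated days would then get 0 - 90 = -90. The only sensible reading is exposure minus untreated days, which is used below.

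**No interruptions**

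SAP formula = L - (E - L) = 2L - E. True value = L. Shortfall = L - (2L - E) = E - L.

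| Last dose L | End of study E | Post-stop days E - L | SAP formula 2L - E | True days | Too low by |
|---|---|---|---|---|---|
| 30 | 30 | 0 | 30 | 30 | 0 |
| 30 | 60 | 30 | 0 | 30 | 30 |
| 30 | 90 | 60 | -30 | 30 | 60 |
| 45 | 90 | 45 | 0 | 45 | 45 |
| 60 | 90 | 30 | 30 | 60 | 30 |

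With E = 90 the total is negative whenever 2L < 90, that is for every L up to 44 (L = 44 gives -2, L = 45 gives 0).

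**Two interruptions, as in the SAP's illustration.** Suppose dosing on Days 1-10, 15-25 and 31-60, with end of study on Day 90.
- Exposure = 60.
- Interruption terms by the SAP's rule (restart date minus stop date) = (15 - 10) + (31 - 25) = 5 + 6 = 11.
- Post-stop term = 90 - 60 = 30.
- SAP formula = 60 - (11 + 30) = 19.
- Without the post-stop term = 60 - 11 = 49.
- True dosing days = 10 + 11 + 30 = 51.

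The total error is 51 - 19 = 32 days. Of these, 30 are the post-stop term, again E - L. The other 2 come from a separate and smaller matter: if the recorded stop date is itself a dosing day, restart minus stop counts one day too many per gap.

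**The case against.** The strongest defence is that the sentence is plainly misworded. Its author may have meant the whole span from first dose to end of study, from which removing all untreated days would give the right answer. That may well have been the intention. The same section, however, defines duration of exposure as ending at the last actual administration, and nothing else in either document overrides that. The text is wrong as written on any reading.

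Three limits on the point do stand:

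- **CRF conventions.** The CRF completion rules are not in the documents. The inconsistency between the two definitions is certain. The exact size E - L depends on the stop date being the last-dose date, and the one-day-per-gap effect also depends on the CRF convention.
- **Probably few subjects.** Planned drop-out is about 10%, and subjects who leave the study are to be seen promptly, so E - L tends to be small for them. The large errors need a subject who stops drug and stays.
- **Limited consequence.** Protocol 12.3 plans no compliance summary, so this is a descriptive item found only in the SAP. The correctly defined duration of exposure and the reasons for stopping treatment are reported beside it.

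These limits bear on the importance of the error, not on whether it exists.

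**Conclusion.** The concern holds, as a minor point. Read as exposure minus untreated days, and with the recorded stop date taken as the last dose, the SAP formula understates days with any treatment by E - L for every subject with a permanent-discontinuation record. The error is nil when the study ends on the last-dose day. It reaches 60 days for a Day 30 stop followed to Day 90, where the reported total is negative. Interruptions leave this component unchanged. No arm-level effect can be given, because the documents state no rate of stopping drug while remaining in the study.

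The damage is confined to one descriptive Safety Set summary. Efficacy analyses, the treatment-emergent adverse event window and the duration-of-exposure summary do not use this total.

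**What to change.** In SAP 2.4.1, define total days with any treatment as duration of exposure minus interruption days only, and delete the permanent-discontinuation term. For a subject with a permanent-discontinuation record, an equivalent form is (end-of-study date - first-dose date + 1) minus all untreated days. In the two-interruption example this gives 90 - 41 = 49, the same as 60 - 11. The first form is simpler and needs no end-of-study date.

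Two wording changes belong with it:
- State that the untreated days are subtracted from the duration of exposure.
- State how an interruption is counted under the CRF's stop-date convention. If the stop date is a dosing day, count one day less per gap, which gives the true 51 in the example.

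The cost is one formula in the SAP and the matching entry in the derived-data specification. No additional data are needed.

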## **6.5 Dose escalation and dose modification**

Investigational or other study treatment dose adjustments and/or interruptions are not permitted.

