## 6.7.2 Instruction for prescribing and taking study treatment

**Table 6-4 Dose and treatment schedule**

Investigational/Control Drug (UNR844-CI/ Placebo)	Dose	Frequency and/or Regimen
UNR844-CI 1.5%	One drop in each eye	Twice-daily
Placebo	One drop in each eye	Twice-daily

Subjects should take the study treatment at approximately the same time each day twice-daily. For example, morning dose at approximately 8AM and evening dose at approximately 8PM. Contact lenses must be removed prior to administering the study treatment. Contact lenses may be worn approximately 15 minutes after administering the study treatment. If a dose is missed and it has been more than 6 hours from the approximate usual time of dosing, subjects should continue with the next scheduled dose.

[figure not shown]
All kits of study treatment assigned by the IRT will be recorded in the IRT system.

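### The SAP's interruption formula counts the dosed restart day as untreated, so days with any treatment come out one day short per recorded interruption

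*SAP*

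**What the plan says.** SAP 2.4.1 plans one compliance measure: "Compliance will be presented by summarizing the total number of days with any treatment by treatment group". It is built from three pieces.

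- **Duration of exposure.** This runs from the first dosing date to the "date of the last actual administration of UNR844-CI or placebo", with 1 added, so both end days count as treated.
- **Days without treatment.** The SAP illustrates these with a subject who has two interruptions and then stops permanently. The interruptions are "Start date of dose after the first dose interruption – stop date of dose before the first dose interruption" and "Start date of dose after the second dose interruption – Stop date of dose before the second dose interruption". The permanent stop is counted from "end of study date – stop date of dose when" permanent discontinuation is recorded.
- **Combination.** The untreated days are summed, "then subtracted by duration of exposure". Taken literally this reverses the order. The evident intent is exposure minus untreated days, and that reading is used below.

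Protocol 6.5 states: "Investigational or other study treatment dose adjustments and/or interruptions are not permitted". The SAP nevertheless provides for interruptions. Deviation TRT02 in SAP 5.3 keeps such subjects in every analysis set, SAP 2.8.1 plans a table of adverse events that led to an interruption, and SAP 2.4.1 works through a case with two.

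**The concern.** The reported quantity is days with any treatment, so a day with a single dose counts as treated. The stop date of the dose before a gap and the start date of the dose after it are, on their ordinary meaning, both such days. Subtracting one date from the other counts every day after the stop date up to and including the restart date, and so puts one dosed day among the untreated ones. The exposure formula in the same section adds 1 so as to include both end dates; the interruption terms make no matching adjustment.

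At stake is the accuracy of the only compliance measure in SAP 2.4.1. The error always lowers the count, and it occurs for every recorded interruption whatever its length.

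**Working it through.** The SAP gives a rule and no numerical result here, so there is no stated figure to reproduce. The check sets the rule beside a direct count of days.

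**Inputs.** From SAP 2.4.1: exposure = last − first + 1; interruption days = restart − stop; post-discontinuation days = end of study − stop. From the schedule in Protocol Table 8-1: Month 3 falls on Day 90. The dosing histories are illustrative.

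**General result.** Let the stop date be the last dosed day before the gap and the restart date the first dosed day after it. The undosed days are stop + 1 to restart − 1, which number restart − stop − 1. The SAP term is restart − stop. The excess is 1, whatever the gap length.

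**One interruption, completer.** Doses on Days 1-10 and 13-90.
- Direct count: 10 + 78 = 88 treated days; Days 11 and 12 are untreated.
- SAP: exposure 90 − 1 + 1 = 90; interruption 13 − 10 = 3; result 90 − 3 = 87.
- With −1: interruption 2; result 90 − 2 = 88.

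**Two interruptions, completer.** Last dose Day 20, restart Day 24; last dose Day 50, restart Day 53; treatment to Day 90.
- Direct count: Days 21-23 and 51-52 are untreated, so 90 − 3 − 2 = 85.
- SAP: 90 − 4 − 3 = 83, which is 2 short for 2 interruptions.
- With −1 in each term: 85.

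**Size.** One day in 90 is 1/90 = 1.1% of the course. Relative to the gap itself, a one-day gap is counted as 2 days, a two-day gap as 3 and a seven-day gap as 8. The documents give no interruption rates. If 5% to 10% of an arm had one interruption each (an assumption), the arm mean would fall by 0.05 to 0.10 day.

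**The other stop-date convention.** Suppose the stop date were the first undosed day. For the gap of Days 21-23 the SAP term is 24 − 21 = 3, which is right. For a subject whose last dose is on Day 70 and whose study ends on Day 90, the discontinuation term becomes 90 − 71 = 19, against 20 untreated days (71-90) if Day 90 is counted. If the stop date is the last dosed day, that term is 90 − 70 = 20, which agrees with the count.

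**A subject like the SAP's own illustration.** The same two gaps, last dose Day 70, end of study Day 90.
- Direct count: 70 − 3 − 2 = 65.
- SAP: 70 − 4 − 3 − 20 = 43, short by 22.
- With −1 in the interruption terms only: 70 − 3 − 2 − 20 = 45, still short by 20.

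The remaining 20 days arise because days after the last dose are deducted from an exposure that already ends at the last dose.

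**The case against.** **The stop date is not defined.** The Study treatment CRF is not part of the documents, and neither document says whether its stop date is the last dosed or the first undosed day. A reader might infer from the section that the interruption and discontinuation terms cannot both be right under any convention. That goes too far. If the stop date is the first undosed day and the end-of-study day is not itself counted as untreated, both terms are correct, and SAP 2.4.1 does not say whether that final day counts. The reading is strained, because it needs a stop date of dose on which no dose was taken and an uncounted final day. It does show that the convention has to be written down along with the −1. Inserting −1 under the other convention would create an error.

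**No differential bias is shown.** A reader might also infer that the error penalises the active arm, since Protocol 4.5 reports eye irritation in 6% on active and 0% on placebo in the prior study. The same list has conjunctival hyperemia in 0% and 8%, the other way round. No interruption rates by arm are given. Protocol 6.5 does not permit interruptions, and 6.5.1 directs subjects who do not tolerate the schedule to discontinuation of treatment. The direction within a subject is certain; a difference between arms is not established.

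**Short lapses may never enter the formula.** Missing one evening dose and the next morning's dose would be counted as one day off with no full day missed (stop Day 20, restart Day 21: 21 − 20 = 1). Nothing shows that such a lapse would be recorded as an interruption, so it adds no weight.

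**The consequence is small.** This stands. The measure is a descriptive Safety Set summary. The primary estimand and the imputation rules in SAP 2.5.1 and 2.5.3 depend on permanent discontinuation and prohibited medication, not on this count.

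**Conclusion.** Wrong as written, minor. On the plain reading of SAP 2.4.1 the dosed restart day is counted as untreated, and total days with any treatment are understated by exactly one day per recorded interruption, about 1.1% of a 90-day course. This rests on the stop date being the last dosed day. That is the ordinary meaning of the words and fits the SAP's discontinuation term when the end-of-study day is counted. Subjects without a recorded interruption are unaffected by this error, and no efficacy test uses the figure.

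It should not be inferred that the −1 alone makes the compliance summary correct for everyone. It does so for subjects who complete treatment. In the discontinued-subject example above, the interruption terms account for only 2 of the 22 missing days.

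**What to change.** In SAP 2.4.1:

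1. State that the stop date is the last day on which any dose was taken. Check this against the CRF field; if the CRF records the first undosed day, derive the last dosed day from it before applying the formula.
2. Replace each interruption term by (start date of dose after the interruption − stop date of dose before the interruption − 1).
3. Write the combination as duration of exposure minus days without treatment, so that the order is clear.
4. For subjects who stop permanently, also correct the deduction of days after the last dose. With exposure as the starting quantity, leaving that term out gives the direct count in the example (70 − 3 − 2 = 65).

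The first two items cost about a line of SAP text and a line of dataset code. The other two are edits to the same paragraph. No new data are needed, and no efficacy analysis changes.
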